### 9.3 VISIT 3: WEEK 1 (DAY 8) DOSE ESCALATION

The following order of procedures is recommended to prioritize safety and efficacy assessments:

1. The Investigator will conduct/administer the following assessments (\*or his/her designee where asterisked):
  - a. Weight\*
  - b. Investigator-administered MADRS followed by the computer-administered MADRS
  - c. Allow patient to complete SHAPS; reviewed by site personnel qualified to oversee completeness\*
  - d. C-SSRS
  - e. CGI-I
  - f. SHSF and if applicable, SHFU
  - g. Concomitant therapies review\*
  - h. Adverse events review

- i. Neurological examination
  - j. Vital signs (BP and pulse both supine and standing, respiratory rate, temperature)\*
2. The rater will administer the FERT
3. Collect and/or monitor digital assessments, as applicable
4. Blood and urine collection for central laboratory analysis (including urine pregnancy test for women of child-bearing potential). Note: blood and urine may be collected earlier in the visit as long as it precedes administration of the FERT by > 1 hour.
5. The patient-returned investigational study drug will be accounted for and patient will be re-instructed if found to be out of compliance
6. Complete IWRS and dispense allocated study drug
7. Collect three blood samples for pharmacokinetic analysis at the following time points: (1) prior to dosing, (2) between 15 min and 2 hours after dosing, and (3) between 4 and 8 hours after dosing
8. After completing the pre-dose pharmacokinetic blood sample, **the patient will take the increased dose of investigational study drug** (i.e., two capsules) with a light snack at the site from the bottle dispensed at this visit
9. Dispense allocated study drug and instruct patient on the importance of compliance and returning the dispensed bottle with any unused study drug at each visit.
10. Instruct all patients to **take two capsules of their assigned study drug daily, and not take study drug the day of their next clinic visit.**

The Investigator will review the results of the central laboratory tests for safety prior to the next visit.

#### 9.4 VISIT 4: WEEK 2 (DAY 15)

The following order of procedures is recommended to prioritize safety and efficacy assessments:

1. The Investigator will conduct/administer the following assessments (\*or by his/her designee where asterisked):
  - a. Weight\*
  - b. Investigator-administered MADRS followed by the computer-administered MADRS
  - c. Allow patient to complete SHAPS and pain question; reviewed by site personnel qualified to oversee completeness\*
  - d. C-SSRS
  - e. CGI-I
  - f. SHSF and if applicable, SHFU
  - g. Concomitant therapies review\*
  - h. Adverse events review
  - i. Neurological examination

- j. Vital signs (BP and pulse both supine and standing, respiratory rate, temperature)\*
2. The rater will administer the FERT
3. Collect and/or monitor digital assessments, as applicable
4. The patient-returned investigational study drug will be accounted for and patient will be re-instructed if found to be out of compliance
5. The Investigator will **assess tolerability and decrease the investigational study drug dose** via IWRS if deemed appropriate
6. Complete IWRS
7. Blood and urine collection for central laboratory analysis (including urine pregnancy test for women of child-bearing potential). Note: blood and urine may be collected earlier in the visit as long as it precedes administration of the FERT by > 1 hour.
8. After completing all study procedures, the patient will take their investigational study drug at the tolerated dose (i.e., either two capsules or one capsule) with a light snack at the site from the bottle dispensed at this visit
9. Dispense allocated study drug and instruct patient on the importance of compliance and returning the dispensed bottle with any unused study drug at each visit.
10. Instruct all patients to take their assigned study drug dose daily, **and not take study drug the day of their next clinic visit.**

The Investigator will review the results of the central laboratory tests for safety prior to the next visit.

#### 9.5 VISIT 5, WEEK 4 (DAY 29)

The following order of procedures is recommended to prioritize safety and efficacy assessments:

1. The Investigator will conduct/administer the following assessments (\*or by his/her designee where asterisked):
  - a. Weight\*
  - b. Investigator-administered MADRS followed by the computer-administered MADRS
  - c. Allow patient to complete HADS, SHAPS, DARS, and pain question; reviewed by site personnel qualified to oversee completeness\*
  - d. HAM-A
  - e. C-SSRS
  - f. CGI-I
  - g. SHSF and if applicable, SHFU
  - h. Concomitant therapies review\*
  - i. Adverse events review
  - j. Neurological examination
  - k. Vital signs (BP and pulse both supine and standing, respiratory rate,

temperature)\*

1. 12-lead ECG\*
2. Blood and urine collection for central laboratory analysis (including urine pregnancy test for women of child-bearing potential)
3. The patient-returned investigational study drug will be accounted for and patient will be re-instructed if found to be out of compliance
4. Complete IWRS
5. The rater will administer the PRT and EEfRT in the order assigned by IWRS
6. Collect and/or monitor digital assessments, as applicable
7. Collect three blood samples for pharmacokinetic analysis at the following time points: (1) prior to dosing, (2) between 15 min and 2 hours after dosing, and (3) between 4 and 8 hours after dosing
8. After completing all study procedures including the pre-dose pharmacokinetic blood sample, the patient will take their dose of investigational study drug from the bottle dispensed at this visit with a light snack at the site
9. Dispense allocated study drug and instruct patient on the importance of compliance and returning the dispensed bottle(s) with any unused study drug at each visit.
10. Instruct all patients to take their assigned study drug dose daily, **and not take study drug the day of their next clinic visit.**

The Investigator will review the results of the central laboratory tests for safety prior to the next visit.

#### 9.6 VISIT 6, WEEK 6 (DAY 43)

The following order of procedures is recommended to prioritize safety and efficacy assessments:

1. The Investigator will conduct/administer the following assessments (\*or his/her designee where asterisked):
  - a. Weight\*
  - b. Investigator-administered MADRS followed by the computer-administered MADRS
  - c. C-SSRS
  - d. Allow patient to complete pain question; reviewed by site personnel qualified to oversee completeness\*
  - e. CGI-I
  - f. SHSF and if applicable, SHFU
  - g. Concomitant therapies review\*
  - h. Adverse events review
  - i. Neurological examination
  - j. Vital signs (BP and pulse both supine and standing, respiratory rate,

temperature)\*

2. Blood and urine collection for central laboratory analysis (including urine pregnancy test for women of child-bearing potential)
3. Collect and/or monitor digital assessments, as applicable
4. The patient-returned investigational study drug will be accounted for and patient will be re-instructed if found to be out of compliance
5. Complete IWRS and dispense allocated study drug
6. After completing all study procedures, the patient will take their investigational study drug with a light snack at the site from the bottle dispensed at this visit
7. Instruct patient on the importance of compliance and returning the dispensed bottle(s) with any unused study drug at each visit.
8. Instruct all patients to take their assigned study drug dose daily **and not take study drug the day of their next clinic visit.**

The Investigator will review the results of the central laboratory tests for safety prior to the next visit.

#### 9.7 VISIT 7, WEEK 8 (DAY 57) END OF TREATMENT

Special effort will be made by the site to encourage patients who discontinue from the study early to complete all Visit 7 (week 8) assessments and safety follow-up visit assessments. If the patient does not attend the discontinuation visit, the C-SSRS should be completed if the site has become aware of a potential suicide-related thought of behavior by other communications. The following order of procedures is recommended to prioritize safety and efficacy assessments:

1. The Investigator will conduct/administer the following assessments (\*or his/her designee where asterisked):
  - a. Weight\*
  - b. Investigator-administered MADRS followed by the computer-administered MADRS
  - c. Allow patient to complete HADS, SHAPS, DARS, and pain question; reviewed by site personnel qualified to oversee completeness\*
  - d. HAM-A
  - e. C-SSRS
  - f. CGI-I
  - g. SHSF and if applicable, SHFU
  - h. Concomitant therapies review\*
  - i. Adverse events review
  - j. Neurological examination
  - k. Vital signs (BP and pulse both supine and standing, respiratory rate, temperature)\*
  - l. 12-lead ECG \*

2. Blood, pharmacokinetic, and urine collection (including urine drug screen and local urine pregnancy test for women of child-bearing potential)\*
3. Collect and/or monitor digital assessments, as applicable
4. The patient-returned investigational study drug will be accounted for
5. Complete IWRS
6. The rater will administer the PRT and EEfRT in the order assigned by IWRS.

The Investigator will review the results of the central laboratory tests for safety prior to the next visit.

## 9.8 VISIT 8, SAFETY FOLLOW-UP

This visit will be conducted approximately 7-14 days after patients complete their study drug. The following order of procedures is recommended to prioritize safety and efficacy assessments:

1. The Investigator will conduct/administer the following assessments (\*or his/her designee where asterisked):
  - a. Weight\*
  - b. Investigator-administered MADRS followed by the computer-administered MADRS
  - c. C-SSRS
  - d. CGI-I
  - e. SHSF and if applicable, SHFU
  - f. Concomitant therapies review\*
  - g. Adverse events review
  - h. Neurological examination
  - i. Vital signs (BP and pulse both supine and standing, respiratory rate, temperature)\*
2. Collect and/or monitor digital assessments, as applicable
3. Blood and urine collection (including local urine pregnancy test for women of child-bearing potential)
4. Any remaining patient-returned investigational study drug will be accounted for
5. Complete IWRS
6. After all study assessments are complete, assist patient to remove digital applications from their smartphone device, as applicable.

Table 1 Schedule of Assessments

Schedule of Assessments	Screening Period	Baseline	Study Drug Treatment				End of Treatment 	Safety Follow-Up
	Visit	2	3	4	5	6	7	8
	Day	D1	D8	D15	D29	D43	D57	
	Week	W0	W1	W2	W4	W6	W8	W9 - 10
Clinician-administered Clinical Assessments								
SCID-CT	X							
CGI-S	X	X						
CGI-I		X	X	X	X	X	X	X
HAM-A		X			X		X	
C-SSRS	X	X	X	X	X	X	X	X
Investigator- and computer-administered MADRS	X	X	X	X	X	X	X	X
Inclusion/exclusion criteria	X	X b						
Neurological examination	X	X	X	X	X	X	X	X
Medical/psychiatric history	X							
Previous and current MDD psychiatric therapy/pharmacologic and non-pharmacologic	X							
Personal history: traumatic events	X							
Demographics & baseline habits	X							
Physical examination	X							
Study Assessments								
Informed consent (before procedures/tests)	X							
Height	X							
Weight	X	X	X	X	X	X	X	X
Complete IWRS	X	X	X	X	X	X	X	X
Study Medication Activities								
Dispense and administer /study drug c		X c1	X c2	X c3	X	X		
Study drug compliance		X	X	X	X	X	X	
Safety Assessments								
Adverse events review		X	X	X	X	X	X	X
Vital signs d	X	X	X	X	X	X	X	X
12-lead ECG	X	X			X		X	
Concomitant therapies review	X	X	X	X	X	X	X	X
SHSF, and SHFU as appropriate	X	X	X	X	X	X	X	X
Urine drug and alcohol screen	X	X					X	
Urinalysis	X	X	X	X	X	X	X	X
Pregnancy Test e	X	X	X	X	X	X	X	X
Hematology	X	X	X	X	X	X	X	X
Clinical chemistry, including Amylase and Lipase	X	X	X	X	X	X	X	X
Thyroid function tests	X							
Hepatitis screen	X							
Hepatic monitoring f	X							

Schedule of Assessments	Screening Period	Baseline	Study Drug Treatment				End of Treatment l	Safety Follow-Up
	Visit	2	3	4	5	6	7	8
	Day	D1	D8	D15	D29	D43	D57	
	Week	W0	W1	W2	W4	W6	W8	W9 - 10
Other Blood Collections								
PK sample		X	X		X		X	
Nonpharmacogenetic biomarker samples		X					X	
Pharmacogenetic sample		X						
ePatient Reported Outcome Assessments								
LICQ	X g							
Pain question		X		X	X	X	X	
HADS		X			X		X	
DARS		X			X		X	
SHAPS		X	X	X	X		X	
Emotional Tasks								
FERT h		X	X	X				
Behavioral Tasks i								
PRT		X			X		X	
EEfRT		X			X		X	
Digital Assessments j								
Collect/monitor digital assessments k	X	X	X	X	X	X	X	X

- a Visit 1 procedures may be completed over 2 days, if necessary and extended for up to 42 days if needed for washout.
- b Eligibility must be re-confirmed prior to randomization.
- c Patients will take their study drug in the clinic from the bottle dispensed that day with a light snack. If a patient discontinues before completing the study drug treatment, an effort should be made to obtain a blood sample at the time of discontinuation
- c1 All patients initiate dosing with 40 mg (one capsule) through week 1
- c2 All patients increase dosing to 80 mg (two capsules)
- c3 The dose may be decreased back to 40 mg (one capsule) anytime through Visit 4 (week 2), if required, for tolerability
- d Collect BP and pulse in supine and standing; collect RR and temperature in any position
- e Serum pregnancy test at Visit 1 (screening) performed by a Sponsor-designated laboratory; urine pregnancy tests will be performed at subsequent visits by the site for all women of childbearing potential (women not surgically sterilized and between menarche and 2 years postmenopausal).
- f Based on laboratory safety values, unscheduled hepatic monitoring testing may be performed as part of patient follow-up, in consultation with the Sponsor-designated Medical Monitor.
- g Patient completes the LICQ before clinician SCID-CT interview.
- h The rater administers the FERT prior to blood draw collections or at least 1 hour after blood draw collection. The FERT should not immediately precede or follow the PRT/EEfRT.
- i As much as possible, schedule the patient to complete the PRT/EEfRT tasks at approximately the same time at all visits where they are conducted. The patient will complete the tasks in the order assigned by IWRS.
- j At the screening visit, assist patient to download, register and launch digital applications on their smartphone device, as applicable.
- k Schedule assignments for patients who have downloaded the app to complete “in clinic” and “out of clinic” vocal samples. Out of clinic assignments should be assigned on a weekday approximately 2-3 days after a clinic visit.
- l Patients who discontinue early from the study should be encouraged to complete the End of Treatment visit assessments. If the patient does not attend the discontinuation visit, the C-SSRS should be completed if the site has become aware of a potential suicide-related thought of behavior by other communications.

## 10 TREATMENT

### 10.1 TREATMENTS ADMINISTERED

This study involves a comparison of BTRX-246040 versus placebo taken orally once daily for 8 weeks. Treatment will be initiated at 40 mg (1 capsule) once daily for approximately one week then will be increased to 80 mg (2 capsules) once daily at Visit 3 (week 1). One dose reduction back to 40 mg (1 capsule) once daily will be allowed through Visit 4 (week 2) for patients who cannot tolerate the 80 mg (2 capsule) dose. Refer to [section 10.5](#) for timing of dose administration. [Table 2](#) shows the treatment regimens.

**Table 2 Treatment Regimens**

Treatment Group	Regimen*
BTRX-246040	40 mg (1 capsule BTRX-246040) orally QD x 1 week, then 80 mg (2 capsules BTRX-246040) orally QD x 7 weeks
Placebo	1 capsule orally QD x 1 week, then 2 capsules orally QD x 7 weeks

\* dose reduction back to 40 mg (1 capsule) once daily will be allowed through Visit 4 (week 2)

The Investigator or his/her designee is responsible for explaining the correct use of the investigational product to the patient and site personnel, verifying that instructions are followed properly, maintaining accurate records of investigational product dispensing and collection, and returning all unused medication to the Sponsor or its designee at the end of the study.

### 10.2 MATERIALS AND SUPPLIES

BTRX-246040 and placebo capsules and packaging will be identical to maintain Investigator and patient blinding. Patients should be instructed to swallow capsules whole and not crush or chew and store the capsules in their original packaging at the temperature listed on the package label. Clinical trial materials will be labeled according to the regulatory requirements.

### 10.3 METHOD OF ASSIGNMENT TO TREATMENT

Patients who meet all inclusion criteria and are subsequently not excluded by the exclusion criteria will be randomized to double-blind treatment at Visit 2 (baseline) using an interactive web-response system (IWRS). Patients will be randomized in a 1:1 ratio to one of two treatment arms (placebo or BTRX-246040 QD). Randomization will be stratified by anhedonia symptom severity, as indicated by SHAPS total score  $\leq 4$  and total score  $> 4$ . The order in which the PRT and EEfRT administrations are conducted will be assigned via IWRS.

The IWRS will be used to assign bottles containing double-blind investigational product or placebo to each patient. Site personnel may be required to confirm that they have located the correct bottles by entering a confirmation number found on the package label into the IWRS prior to dispensing the bottle(s) to the patient (see [section 10.5](#)).

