### 6.2 SECONDARY OBJECTIVES

- To evaluate the effects of BTRX-246040 on anhedonia in adult patients with MDD
- To evaluate the safety and tolerability of BTRX-246040 in adult patients with MDD
- To evaluate the effects of BTRX-246040 on the performance of tasks as measured by the Facial Expression Recognition Task (FERT), Probabilistic Reward Task (PRT), and Effort Expenditure for Reward Task (EEfRT) in adult patients with MDD

[figure not shown]

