8. Proportion of patients who demonstrate significant clinical improvement, where **improvement** is defined by a score of 1 (very much improved) or 2 (much improved) on the CGI-I at Week 8.

The following secondary efficacy endpoints based on the performance tasks will be analyzed and presented in summary and graphical displays.

Data for the FERT will be summarized (mean, standard deviation, range) for each treatment group at each visit. All treatment differences will be estimated with 95% CI. No adjustments will be made for multiple comparisons. The analysis will employ ANOVA models without adjusting for covariates. However, if significant confounds are identified, a secondary analysis will be performed to examine the relationship between FERT outcome measures and other covariates. A full description of the statistical analysis methods for FERT outcome measures will be provided in in the SAP.

9. Outcome measures from the FERT
  - a) Accuracy
  - b) Misclassification
  - c) Average reaction time
  - d) Target sensitivity
  - e) Response bias

Data for all PRT outcome measures will be summarized (mean, standard deviation, range) for each treatment group at each visit. The ANOVA models will be used to compare between treatment groups. For “Response bias” and “Discriminability,” treatment group, block, and treatment-by-block interactions will be considered fixed effects. For “Reaction time” and “Hit rates,” the stimulus type will be included as an additional fixed effect. The details of the analysis methods for these outcome measures will be described in the SAP.

10. Outcome measures from the PRT

- a) Response bias
- b) Discriminability
- c) Reaction time
- d) Hit rates

Data for all EEfRT outcome measures will be summarized (mean, standard deviation, range) for each treatment group at each visit. Statistical analyses of the Preference during the EEfRT trial will be performed using Generalized Estimating Equation (GEE) models. A binary logistic distribution will be used to model the probability of the Preference. The relationship and interactions between Preference and independent variables of reward magnitude, reward probability, expected value, age, sex, and efficacy parameters will be explored. The ANOVA model will be used to compare the completion rates between treatment groups. The details of the analysis method for these outcome measures will be described in the SAP.

11. Outcome measures from the EEfRT

- a) Preference (hard or easy task choice)

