15.2.3.9. Probabilistic Reward Task

Each outcome measure of the PRT will be summarized (mean, standard deviation, median, and range) at each visit. Response bias and discriminability will be summarized by block and treatment. Reaction time and hit rates will be summarized by stimulus (rich vs. lean), block and treatment. Line plots of means (+/-SD) will also be presented by treatment group and visit.

At each scheduled visit, an ANOVA model will be used to compare treatment groups. The models for response bias and discriminability will include terms for treatment, block, and treatment-by-block will be used to analyze treatment differences. The models for reaction time and hit rates will include terms for treatment, block, stimulus, and treatment-by-block will be used to analyze treatment differences. The models LS Means and standard errors (SEs) will be presented for each treatment group. The difference in LS Means with corresponding SEs, 95% confidence intervals for differences, and p-values will also be presented. No adjustments will be made for multiple comparisons.

All data, including the overall total scores, will be listed by treatment and patient.

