15.2.3.10. Effort Expenditure for Reward Task

Each outcome measure of the EEfRT will be summarized (mean, standard deviation, median, and

---

Document:	C:\Users\q718413\Documents\NEP-MDD-201_SAP_v1.0_Final_06Dec2018.docx		
Author:	[name]	Version Number:	1.0
		Version Date:	06Dec2018

Template No: CS\_TP\_BS016 Revision 4  
Effective Date: 01Apr2016

Reference: CS\_WI\_BS005

Analysis Plan

---

range) by treatment group at each visit. Line plots of means (+/-SD) will also be presented by treatment group and visit.

The analysis of completion rates will use an ANOVA model with a term for treatment to analyze treatment differences at each scheduled visit. The models LS Means and standard errors (SEs) will be presented for each treatment group. The difference in LS Means with corresponding SEs, 95% confidence intervals for differences, and p-values will also be presented. No adjustments will be made for multiple comparisons.

The analysis of preference will be completed utilizing Generalized Estimating Equation (GEE) models. A binary logistic distribution will be used to model the dichotomous outcome of preference at each scheduled visit. At each visit a series of models using a variety of factors will be fit. All models in the series will include explanatory variables reward magnitude, reward probability, and expected value (reward magnitude X probability) as a base. For each series, four models will be fit. The first will include the base variables with the additional variable of interest with no interactions. The next three models will include the same but with an interaction term between the variable of interest and each base variable in order. The variables of interest that will be explored include:

- Age
- Sex
- Treatment
- MADRS Total Score
- SHAPS Score (0 – 14 scoring method)
- DARS Total Score

The parameter estimates, standard error, 95% confidence interval, degrees of freedom and p-values will be presented to for each model.

All data will be listed by treatment and patient.

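### The system-assigned order of the PRT and EEfRT is left out of every model for the two tasks; adding it is a cheap, probably small gain in precision

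*Protocol*

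**What the plan says.** Protocol 10.3, just after the randomization and stratification rules, states: "The order in which the PRT and EEfRT administrations are conducted will be assigned via IWRS". Table 1, footnote i, adds: "The patient will complete the tasks in the order assigned by IWRS". The procedures for Visits 2, 5 and 7 (Protocol 9.2, 9.5 and 9.7) and the task descriptions (11.1.8 and 11.1.9) repeat the instruction. Performance on both tasks is part of a secondary objective (Protocol 6.2; SAP 2.2).

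The models are specified as follows:

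- **PRT response bias and discriminability.** Protocol 13.2.8.3: "treatment group, block, and treatment-by-block interactions will be considered fixed effects". SAP 15.2.3.9: "The models for response bias and discriminability will include terms for treatment, block, and treatment-by-block".
- **PRT reaction time and hit rates.** SAP 15.2.3.9: "The models for reaction time and hit rates will include terms for treatment, block, stimulus, and treatment-by-block will be used to analyze treatment differences".
- **EEfRT completion rate.** SAP 15.2.3.10: "The analysis of completion rates will use an ANOVA model with a term for treatment".
- **EEfRT preference.** SAP 15.2.3.10 specifies logistic GEE models with reward magnitude, reward probability and expected value, plus one variable of interest from six (age, sex, treatment, MADRS, SHAPS, DARS).

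Order is in none of these. It is also absent from the covariate list in SAP 7.1, from the descriptive summaries of the two tasks and from the subgroup table in SAP 15.3.4.

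**The concern.** A central system sets which task comes first, treatment cannot alter that setting, and the analysis never uses it. If performance depends on which task comes first, the ANOVA models leave that variation in the residual, and any difference between arms in the share of patients taking the PRT first stays in the treatment comparison.

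Three features of the plan mean that the omission is not neutralized elsewhere:

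- The PRT and completion-rate models are fitted visit by visit without the patient's baseline task result, so an order effect that is stable over visits is not removed by baseline adjustment.
- The validity checks in SAP 15.2.1.9 and 15.2.1.10 drop patients from the task analyses, so balance at assignment, if there was any, need not survive in the analysed set.
- The FERT gets a second, covariate-adjusted ANOVA (SAP 15.2.3.8). The PRT and the EEfRT completion rate get none.

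At stake is some precision for nominal secondary results, and the credibility of an order adjustment if one were first proposed after unblinding.

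**Working it through.** **The plan's only related figure.** Protocol 13.1 gives 44 per arm, effect size 0.5, two-sided alpha 0.10 and 75% power. The exact t calculation (86 df) gives 75.2% and the normal approximation 75.8%, so the figure reproduces. It belongs to the MADRS, and task order does not touch it. The documents give no SD, power or order effect for the PRT or EEfRT.

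**Precision, one continuous record per patient (for example the completion rate).** Assume that order shifts the outcome by g within-order SDs, with half the patients in each order and order balanced across arms.

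- Variance added by order: g²/4, on a within-order variance of 1.
- Share of total variance: R² = (g²/4) / (1 + g²/4).
- Standard error with the order term relative to without it: 1/√(1 + g²/4).

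To show what this means for power, I borrow 44 per arm, d = 0.5 and alpha 0.10 from the MADRS calculation. With adjustment, d becomes 0.5/√(1 − R²) and one degree of freedom is lost.

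| Assumed g | 1 + g²/4 | R² | Cut in SE | Power without to with order term |
|---|---|---|---|---|
| 0 | 1.0000 | 0% | 0% | 75.2% to 75.2% |
| 0.2 | 1.0100 | 1.0% | 0.5% | 75.2% to 75.6% |
| 0.3 | 1.0225 | 2.2% | 1.1% | 75.2% to 76.0% |
| 0.5 | 1.0625 | 5.9% | 3.0% | 75.2% to 77.4% |

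The second column also gives the equivalent sample-size ratio: about 1%, 2% and 6% more patients for g of 0.2, 0.3 and 0.5. Nothing in the documents caps g. At 0.8 or 1.0 SD the power with adjustment would be 80.5% or 83.1%.

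**Chance imbalance.** If order is assigned independently of arm but not balanced within it, the between-arm difference in the share taking the PRT first has SD √(2 × 0.25/44) = 0.107, so its 95% range is about ±0.21. Multiplying by g gives the shift in the treatment contrast: 0.2 × 0.209 = 0.04 SD, or 0.5 × 0.209 = 0.10 SD. The contrast's own standard error is about √(2/44) = 0.21 SD. The shift has expectation zero.

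**Where the arithmetic stops.** PRT records are per block, and per block and stimulus for reaction time and hit rates. A patient-level order effect there acts on several correlated records, so the table does not give the change in their standard error. The preference model is a logistic GEE with no residual error variance to reduce. Leaving out a balanced covariate there changes the marginal odds ratio, usually toward the null, and adding it changes what the odds ratio measures.

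**The case against.** The strongest reply is that this is a preference and not an error. The documents report no order effect, and if there is none the gain is nil. The task analyses are nominal, without multiplicity control or a power claim, in a Phase 2a trial. Protocol 13.2.1 already provides for listing IWRS data and for further exploratory analyses, so an imbalance could be noticed if order is among the listed data. All of this stands, and it keeps the point minor. It does not explain why a factor the system assigns is absent from every model.

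Three stronger readings are tempting, and the documents do not support them:

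- **That order is a declared design factor, controlled because of fatigue or reward carry-over.** The protocol does keep the FERT apart from these tasks and asks for a similar time of day, but it gives no such reason for the order. The only stratification factor it names is the SHAPS score.
- **That the treatment contrast is biased.** Under assignment independent of arm, chance imbalance averages to zero, and its likely size is well inside the contrast's standard error. Silence about balance is not evidence of imbalance.
- **That the precision gain applies to all the task outcomes.** It was derived for one continuous record per patient only.

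**Conclusion.** The point holds as a low-cost improvement. The omission is plain from the text: order is assigned by IWRS and enters no PRT or EEfRT model. For the completion rate, the loss is about 0.5% to 3% of the standard error, or about 0.4 to 2 points of illustrative power, over an assumed order effect of 0.2 to 0.5 SD. This rests on roughly equal numbers in each order, balance across arms, and a sample size and effect borrowed from the MADRS calculation. No figure can be given for the PRT models or the preference GEE from what the documents contain. The absence of systematic bias rests on order being assigned independently of arm, which the documents neither state nor contradict.

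**What to change.** 1. SAP 15.2.3.9: add IWRS-assigned order (PRT first or EEfRT first) as a fixed effect in all four PRT ANOVA models.
2. SAP 15.2.3.10: add it as a fixed effect in the completion-rate ANOVA, and as a covariate in the preference GEE models whose variable of interest is treatment. State that the odds ratio in those models is conditional on order. The other five series of preference models can stay as they are, so four of the 24 models per visit (six variables times four models) change.
3. State in the SAP how IWRS assigns order: randomized or not, balanced within arm or not, and fixed or reassigned across visits. If it can change, each visit's model should use that visit's order. If every patient has the same order, there is no term to fit, and a sentence saying so is enough.

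The cost is one degree of freedom per model, bringing one IWRS variable into the analysis data, and minor reprogramming. The change should be settled before unblinding.
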